7.2 Statistical Methods

Standard statistical methods will be used in this study. Parametric analysis will most likely be applied to compare the gadolinium enhancement in the patient's brain before and after BBB opening through paired Student's t-test. However, the statistical analysis will be subject to the results obtained and other methods may be used as well, such as non-parametric statistical tests.

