The neurologist on the study, [name], MD at the Taub Institute of Alzheimer's Disease and Aging at Columbia, will be guiding this clinical application. The subjects will first be diagnosed at Columbia. Six (6) patients will be asked to participate in this initial safety and feasibility study. The subjects will have to meet at least the following criteria: 1) 50 years old or older, 2) have been diagnosed with early AD or mild cognitive impairment (MCI) at minimum and 3) ability to provide informed consent. Approvals and consent forms approved by the Clinical Trials Office (CTO) and the Institutional Review Board (IRB) of Columbia University will be obtained through an IRB approved study (CTO will guide the pre-IDE approval in the first year). All subjects agreeing to participate will undergo the following series of procedures: 1) a high-resolution MRI (without gadolinium contrast agent) will be acquired prior to BBB opening on the GE SIGNATM Premier (3T) (same scanner as in the NHP study) for pre-treatment planning and screening purposes. Also, a PET/CT scan with Amyvid (18F-Florbetapir) will be performed on the SIEMENS Biograph 64 to assess the baseline amyloid plaque load before the treatment. 2) BBB opening will be attempted (in a designated facility in Radiology) using the clinical FUS system. First, a baseline signal will be acquired by applying ultrasound prior to microbubble injection. Then, an intravenous injection of Definity microbubbles under the FDA guidelines will be administered as a bolus or via a syringe pump and cavitation signal will be monitored and recorded during sonication at parameters under the FDA safety guidelines. 3) A MRI (with and without gadolinium) will be acquired immediately after the sonication in order to assess the BBB opening and safety. 4) A follow-up MRI (with and without gadolinium) will be conducted 3 days (±1 day) after the treatment to confirm BBB closing and/or safety. Also, two follow-up PET/CT scans using Amyvid (¹⁸F-Florbetapir) will be conducted 3 weeks (±1 week) and 3 months (± 2 weeks) post-FUS to assess amyloid plaque load.

MRI will be performed at the Neurological Institute of New York / CUMC.

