5.6 Packaging

The ultrasound transducer and the associated electrical components, i.e. function generator, power amplifier, and hydrophone, will be gathered in a mobile cart. The Vantage system with a linear array probe also will be in another mobile cart. All components will be connected prior to the patient's arrival and will be checked by two investigators to ensure smooth operation and safety.

The neuronavigation system along with the accompanying equipment, i.e. infrared camera, reflecting beads, holders etc., will be packed separately and gathered in a mobile cart. The parts will be assembled following the patient's arrival and the imaging beads will be attached to the patient's head and the transducer to allow for real-time neuronavigation.

New packages of Definity microbubbles will be shipped from Lantheus Medical Imaging Inc and will be used in conjunction with the ultrasound transducer to temporarily open the BBB. Definity microbubbles will be freshly activated before sonication and will be withdrawn using a 1-ml syringe to reach the clinical dose (10 μ l/kg) right before the IV injection.

New packages of Dotarem will be shipped from Guerbet LLC. Dotarem will be used as an MRI contrast agent to detect areas in which the BBB has opened. It will be administered according to manufacturer's guidelines at the recommended dose (0.2 ml/kg).

All study drugs will be provided free of charge to research participants.

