5.8.4 Return or Destruction of Study Device

The device should be returned to the following address if damaged: [name].

6 Study Procedures

After patient screening based on the selection criteria, the eligible patients will sign the consent form and fill the information form for the study, be scanned in the MRI for treatment planning, and then the sonication procedure. [name], MD at the Taub Institute of Alzheimer's Disease and Aging at Columbia, will be guiding this clinical application. The subjects will first be diagnosed and referred to the Presbyterian Hospital at Columbia University Medical Center. Six (6) patients will be asked to participate in this initial feasibility and safety study. The subjects will have to meet the following criteria: 1) 50 years old or older,

2) diagnosis of early AD or MCI at minimum (assessing criteria described in section 4.1), and 3) ability to provide informed consent. Approvals and consent forms approved by the Clinical Trials Office (CTO) and the Institutional Review Board (IRB) of Columbia University will be obtained through an IRB approved study.

6.1 Visit 1

All subjects agreeing to participate will undergo the following series of procedures in 4 or 5 visits. In the first visit, a high-resolution MRI scan (without gadolinium contrast agents) will be acquired prior to BBB opening on the 3T MRI for pre-treatment planning and screening purposes. Also, a blood draw and a PET/CT scan with Amyvid (¹⁸F-Florbetapir) will be performed to assess the baseline biomarkers and amyloid plaque load and before the treatment.

6.2 Visit 2

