In the second visit, BBB opening will be attempted in a designated facility in the hospital using the described FUS system. First, a baseline cavitation signal will be obtained prior to microbubble injection. Then, an intravenous injection of Definity microbubbles under the FDA guidelines will be administered as a bolus or via a syringe pump and the cavitation signal will be monitored and recorded during sonication at acoustic parameters well below the FDA safety limit (MI = 0.4). In this EFS, we will target the prefrontal cortex (PFC). PFC has been shown to be affected by AD pathology, leading to deficits in attention, spatial memory and planned movements. Although we do not aim to treat AD in this EFS, PFC was selected as the targeted structure due to its relevance to this condition, its size and ease of targeting with our singleelement transducer. A follow-up MRI (with and without contrast) will be acquired the same day after BBB opening to ensure treatment safety and efficacy. Finally, two blood samples will be collected before and after treatment through an intravenous catheter or a finger prick. Blood analysis will be performed to test whether there are acute changes in the blood test results due to the FUS application. Based on our animal studies, there is an acute increase in reticulocytes, platelets and eosinophils after FUS treatment, possibly due to the BBB restoration process. Blood samples will be used to test whether these changes in blood chemistry occur also in humans. Blood samples will be stored and analyzed to detect potential changes in Alzheimer's Disease biomarkers and other compounds that may exit the brain parenchyma because of the blood-brain barrier opening (e.g. exosomes). All time points will be compared to baseline acquired during screening.

6.3 Visit 3

A follow-up MRI (with and without contrast) will be performed three days (± 1 day) after treatment to confirm BBB closure and to assess safety. A blood sample will be collected through an intravenous catheter or a finger prick, to test for short-term changes in blood chemistry and cell count.

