7.1 Sample Size Determination

Successful methodology will be concluded if the BBB opening is safely opened in the PFC region in at least 75% of the cases as evidenced on MRI. The scan with the BBB opening will be compared to the scan before BBB opening for each patient. The data will be statistically analyzed with parametric paired Student's t-test. Power analysis shows that for a detectable difference of 200 mm³ (after BBB opening - before BBB opening) and a standard deviation of 50 mm³, at least 6 subjects are needed to report a result at the level of α =0.05 and Power=0.95.

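### The paired test of gadolinium enhancement before versus after opening has no baseline value, because no contrast MRI is scheduled before sonication; the text also gives no criterion for calling a patient opened

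*Combined protocol and SAP*

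**What the plan says.** - **Test.** Section 7.2 expects to "compare the gadolinium enhancement in the patient's brain before and after BBB opening" with a paired Student's t-test, and leaves room for other methods, including non-parametric ones.
- **Reference and sample size.** Section 7.1 states "The scan with the BBB opening will be compared to the scan before BBB opening for each patient". It powers an after-minus-before difference of 200 mm³ with SD 50 mm³, alpha 0.05 and power 0.95, and concludes that six subjects are needed. It does not itself mention gadolinium.
- **Scan before opening.** Section 3.1: "a high-resolution MRI (without gadolinium contrast agent) will be acquired prior to BBB opening". Section 6.1 (Visit 1): "a high-resolution MRI scan (without gadolinium contrast agents) will be acquired prior to BBB opening".
- **Scans with contrast.** Section 6.2 (Visit 2): "A follow-up MRI (with and without contrast) will be acquired the same day after BBB opening". Section 6.3 (Visit 3): "A follow-up MRI (with and without contrast) will be performed three days (± 1 day) after treatment to confirm BBB closure".
- **Role of contrast.** Section 5.6: "Dotarem will be used as an MRI contrast agent to detect areas in which the BBB has opened".
- **Second reference.** Section 5.7 says that safety and effectiveness will be judged against the contralateral site. Section 7 does not mention it.
- **Decision rules.** Success under 7.1 is safe opening "in at least 75% of the cases as evidenced on MRI". Section 8.5 sends the protocol back to FDA if three subjects are not successfully opened.

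**The concern.** A paired test needs the same quantity measured twice in each patient. Here the quantity is gadolinium enhancement, and the scan meant to supply the first value is specified as having no gadolinium. The only test named for the imaging endpoint, which carries the primary endpoint of feasibility, therefore lacks one of its two inputs.

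A related gap concerns classification. The 75% rule and the 3-subject trigger count patients as opened or not opened, but the supplied text gives no volume, intensity or reader criterion. The 200 mm³ in 7.1 is a mean difference used for power, not a cut-off for an individual patient. With so few patients, one borderline reading can decide whether the success rule is met.

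**Working it through.** **1. Which scans can supply the test**

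| MRI | Contrast | Source |
|---|---|---|
| Before opening | No | 3.1, 6.1 |
| Same day, after sonication | With and without | 3.1, 6.2 |
| Day 3 (±1) | With and without | 3.1, 6.3 |

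No row gives enhancement before opening. Replacing the t-test by a paired rank test changes nothing, since it uses the same within-patient difference.

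**2. The plan's sample size**

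Inputs from 7.1: difference 200 mm³, SD 50 mm³, alpha 0.05, target power 0.95. Sidedness is not stated; two-sided is assumed. SD 50 is read as the SD of the paired difference. Then d = 200/50 = 4, and power comes from the noncentral t distribution with n−1 degrees of freedom and noncentrality d√n:
- n=3: 0.908
- n=4: 0.998
- n=6: above 0.999

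If SD 50 is instead the SD of a single scan, with zero correlation between scans, the SD of the difference is 50√2 = 70.7 mm³, and n=4 still gives 0.950. The stated six is conservative on either reading.

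**3. Room for a different difference at n=6**

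Power of 0.95 at n=6 needs d = 1.867, so the largest tolerable SD of the difference is:
- 200 mm³: 200/1.867 = 107 mm³
- 150 mm³ (25% of a 200 mm³ opening still present at day 3): 150/1.867 = 80 mm³
- 100 mm³ (50% still present): 100/1.867 = 54 mm³

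The residual fractions are assumptions.

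**4. What the 75% rule means in patients**

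If all six are analysed, 0.75 × 6 = 4.5, so at least 5 of 6 are needed (83%; 4 of 6 is 67%). Section 7.3 defines a protocol-compliant population. If only four patients were in it, 0.75 × 4 = 3, so 3 of 4 would do.

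As an illustration of the missing cut-off c, assume that patients' volumes are Normal(200, 50). Then p = 1 − Φ((c − 200)/50) and P(at least 5 of 6) = 6p⁵(1 − p) + p⁶:
- c = 100 mm³: p = 0.977, P = 0.993
- c = 150 mm³: p = 0.841, P = 0.756
- c = 200 mm³: p = 0.500, P = 0.109

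**5. Limits of the side-to-side replacement**

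Simulated rejection rate of the two-sided 5% paired t-test, n=6, no opening, gamma-distributed background with SD 25 mm³ on each side. All values, including the correlation between sides (Gaussian copula), are assumed.

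| Mean background, mm³ | Correlation 0 | 0.5 | 0.8 |
|---|---|---|---|
| 50 vs 50 | 0.05 or below | 0.05 or below | 0.05 or below |
| 55 vs 45 | 0.09 | 0.14 | 0.26 |
| 62.5 vs 37.5 | 0.33 | 0.54 | 0.85 |

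The test holds its level when the sides have equal mean background. A systematic difference between sides inflates it, and more so when the sides are correlated.

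**The case against.** The strongest reply is that this is a six-patient, single-arm feasibility study. Section 7.2 is tentative about its test, and the post-sonication contrast scan will show an opening whether or not a t-test is run. Much of that stands. A reader might infer that the trial cannot detect opening; the documents do not support this, because the contrast scan after sonication can show it. A reader might infer that six patients are too few; the plan's own inputs say otherwise.

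Two further inferences go too far. One is that the reference would have to be picked after the images are seen. Nothing forces that: 5.7 already names a usable reference, and one can be fixed in advance. The other is that 5.7 and 7.1 contradict each other. A longitudinal and a contralateral comparison can coexist; the fault is that section 7 relies on the one without contrast and omits the one the scans can supply.

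It can also be said that the meningeal-enhancement exclusion in 4.2 implies contrast imaging beforehand, or that the baseline is simply zero. The exclusion does not schedule a contrast scan, and the documents nowhere say that a zero would be entered. Finally, a criterion for opening may exist in the animal study report cited as appendix 6.1, which is not part of the supplied text. The claim is therefore limited to the text at hand.

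**Conclusion.** The point holds: the test in 7.2 cannot be computed from the scheduled scans, and the supplied text does not define opening for the two rules that count it. The size is modest. The sample size stands, and neither the 75% rule nor the 3-subject trigger uses the t-test. The missing criterion is the more consequential part, because the success rule can turn on one patient; the 5-of-6 reading assumes that all six are analysed. The schedule mismatch rests on the text alone and needs no assumption. The power figures assume a two-sided test. The cut-off, asymmetry and residual-opening figures are illustrations under assumed values and are not estimates of this trial's error rates.

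**What to change.** 1. In 7.1 and 7.2, replace the before-versus-after comparison with enhancing volume in the sonicated prefrontal cortex minus that in the mirrored contralateral region, on the same post-sonication contrast MRI. Use one threshold for both sides, fixed in advance, and record the sonicated side, which 6.2 does not give.
2. Report post-sonication minus day-3 enhancement at the target as supportive.
3. If the planned target lies too near the midline for a clean mirrored region, make the day-3 difference the main comparison. Take that decision at treatment planning, before any sonication and for all patients.
4. Restate the 200 and 50 mm³ inputs for the chosen difference.
5. Use the same measure to classify each patient as opened for the 75% rule and the 8.5 count, with the cut-off fixed before the first treated scan is read. State which patients form the denominator.

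The cost is wording in 7.1, 7.2 and 8.5 and one extra region per scan, with no new scan or contrast dose. Two limits should be stated with it. Systematic left-right asymmetry biases the side-to-side test; the day-3 difference checks for this because it uses the same region, provided background is stable between scans. The day-3 difference is in turn conservative if some opening remains: 1.3 reports closure between 2 and 4 days in non-human primates (1.5.1 says within 3 days), and the scan window runs from day 2 to day 4.

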7.3 Subject Population(s) for Analysis

Protocol-compliant population: Any subject who was randomized and received the study device and complied with all protocol required processing

8 Safety and Adverse Events

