5.3 Allocation to Treatment

This is a single arm, non-random trial.

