8.5 Stopping Rules

Redundant safety features have been added to the hardware of the device, as grounding for the transducer, safety switch for the amplifier and function generator. Additionally, we will incorporate safety valves in our software. For any signs showing safety risk including high cavitation dose in the acoustic monitoring or unstable vital signs, the device can be stopped from the computer user interface and/or an emergency stop button. Treatment will be stopped in the case of any reaction of the subject to the ultrasound exposure or microbubble infusion. Pulse oximetry will be used during MRI scans to mitigate the risk of anaphylactic reaction to MRI contrast agents. Potential adverse effects have been grouped according to their severity in the following table:

Severity	Adverse effect			
Severe	Local hemorrhage	Edema	Intracranial infection	Status epilepticus
Moderate	Emesis	Dizziness	Allergic reaction	Nausea
Mild	Skull heating	Injection site bruising	Headache	

The investigation will be paused and the relevant authorities will be notified in case of any death, life threatening event, or any other serious adverse event described in the table above (including disability or clinically significant manifestation of local hemorrhage or edema) due to the procedure. An episode of status epilepticus during treatment will terminate the session immediately.

If the selected ultrasound settings (i.e., MI of 0.4) do not successfully open the BBB in 3 subjects, FDA will be contacted via a submission of an IDE supplement, to discuss revising the protocol's focused ultrasound parameters or increase the number of subjects.

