8.6 Medical Monitoring

Medical monitoring will be performed by the neurologist of this study, [name], MD at the Taub Institute of Alzheimer's Disease and Aging at Columbia. [name] or any other trained radiologist will be present during the trial and will assess the subject's clinical status during therapy. In the case of an allergic or any other reaction (e.g. status epilepticus) to the therapy, the study will be immediately discontinued. Resuscitation equipment will be readily available in the study room, in case of a serious adverse event.

Subjects will be monitored with follow-up MRI scans to confirm BBB opening and closing and PET scans to estimate amyloid plaque load. Should the MRI or PET brain scans of this study have incidental findings (e.g. brain tumor, subarachnoid hemorrhage, or structural abnormality) the subject will be immediately withdrawn from the study and directed for clinical care. MRI scans will be examined by [name], who is a certified in Diagnostic Radiology and is the Section Chief of Neuroradiology. MRI scan examination by [name] will occur as soon as possible but no later than two weeks following receipt of the image.

If there are any incidental findings deemed by the clinical-investigator to be "life-threatening" or "important but not severe", both the subject and the subject's personal primary care physician will be notified. Communication may be initially verbal, followed by a formal written communication. The significance of the incidental finding will be determined by the clinical-investigator and communicated to the subject accordingly. Incidental findings of clinical significance and the management of such findings should be documented in the research records of this study.

At the time of a continuing review, if incidental findings were noted during the previous approval period, the principal investigator of this study will provide the IRB with the following information: the number of required review images, a list of the subject study numbers, the type of scan, the date of the scan, a description of the incidental finding of clinical significance, the date of communication with the subject and the outcome, if known.

If the participants expressed severe depression or suicidal ideation in the course of their visit, the subject will be urgently assessed by the study clinician and appropriate referrals will be made. In addition, we will exclude the participant from the study.

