8.6.1 Data Monitoring Committee (if applicable)

The safety of the BBB opening using ultrasound and microbubbles has been confirmed by previous nonhuman primates studies, which revealed no adverse effects, permanent damage, or behavioral change following repeated treatments using low-intensity ultrasound and clinically-relevant microbubble doses. Ongoing clinical trials using this technique have not reported any acute adverse effect in either of the participants. However, long-term effects in the human brain have not been investigated to date.

To ensure the long-term safety in our study, the investigators will monitor and collect the data for processing and analysis while [name] will be present to assess the safety of the patient during FUS application. [name] will be present during the trial and will assess the subject's clinical status during therapy. In the case of an allergic or any other reaction to the therapy, the study will be immediately discontinued. Resuscitation equipment will be readily available in the study room, in case of a serious adverse event. Subjects will be monitored with follow-up MRI scans to confirm BBB opening and closing. BBB opening will be confirmed with an MRI scan immediately after the ultrasound treatment, while BBB closing will be confirmed three days later. Additional clinical evaluation will be performed by [name] or any other trained neurologist 3 months after the ultrasound treatment. Should the MRI brain scans of this study have incidental findings (e.g. brain tumor or potential structural abnormality) the subject will be immediately withdrawn from the study and directed for clinical care. Incidental findings will be communicated with both the subject and the subject's personal primary care physician.

Cognitive function will be assessed by [name] using appropriate tests before, during, and after the treatment.

9 Data Handling and Record Keeping

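### The only analysis population (7.3) requires randomization in a trial that does not randomize, and the 75% success rule (7.1) leaves its denominator undefined

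*Combined protocol and SAP*

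**What the plan says.** All references are to the combined protocol and SAP.

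- **7.3 Subject Population(s) for Analysis** gives one population, labelled protocol-compliant: "Any subject who was randomized and received the study device and complied with all protocol required processing". No all-treated, safety or evaluable set is defined.
- **5.3 Allocation to Treatment**: "This is a single arm, non-random trial".
- **7.1 Sample Size Determination** concludes success if the barrier is "safely opened in the PFC region in at least 75% of the cases as evidenced on MRI". It does not say whether *cases* are enrolled, treated, scanned or compliant subjects, and it does not define *safely*.
- **3.1 General Design**: "Six (6) patients will be asked to participate in this initial safety and feasibility study".
- **8.5 Stopping Rules**: "Treatment will be stopped in the case of any reaction of the subject to the ultrasound exposure or microbubble infusion". Section 4.4.1 allows withdrawal at any time, and 8.6 requires withdrawal when a study scan shows an incidental finding.
- **5.7 Blinding of Study** says that nothing is blinded.

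**The concern.** The 75% rule is the plan's only numerical success criterion; the primary endpoint in 3.2 simply names feasibility. Its denominator can be read in two ways, and nothing fixes the choice before results are seen in an unblinded study of six.

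The readings differ only for a subject who was treated but did not complete the protocol. Take someone whose session is stopped for a reaction, or who is withdrawn after treatment and so misses the day-3 MRI or the later PET visits. Because success means a *safe* opening, that subject could be scored as not successful, or could be left out as non-compliant. Section 7.3 does not say whether a stop that the protocol itself requires counts as compliance. With six subjects, one such decision can settle the trial's conclusion.

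Two groups do not create the problem. Subjects withdrawn before treatment never received the device, so they enter neither reading. A barrier that fails to open after a completed session is not non-compliance, so that subject stays in under both.

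**Working it through.** **Inputs.** Six planned subjects (3.1) and a pass mark of 75% (7.1). No event rates are assumed, because the documents give none for stops or withdrawals.

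**The literal set.** 7.3 requires randomization, receipt of the device and full compliance, all three together. By 5.3 nobody is randomized, so the set is empty. Without the first condition it holds treated, fully compliant subjects only.

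**Pass mark with all six treated as denominator.** 0.75 × 6 = 4.5, so 5 successes are needed: 5/6 = 83% passes and 4/6 = 67% fails.

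**One treated subject excluded.** Let S be the number of safe openings among six. The result is S/5 if a non-success is excluded and (S − 1)/5 if a success is.

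| S | All six | Non-success excluded | Success excluded |
|---|---|---|---|
| 0 | 0/6 fail | 0/5 fail | not possible |
| 1 | 1/6 = 17% fail | 1/5 = 20% fail | 0/5 fail |
| 2 | 2/6 = 33% fail | 2/5 = 40% fail | 1/5 = 20% fail |
| 3 | 3/6 = 50% fail | 3/5 = 60% fail | 2/5 = 40% fail |
| 4 | 4/6 = 67% fail | **4/5 = 80% pass** | 3/5 = 60% fail |
| 5 | 5/6 = 83% pass | 5/5 pass | 4/5 = 80% pass |
| 6 | 6/6 pass | not possible | 5/5 pass |

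There are 6 + 6 = 12 feasible cases. One changes the conclusion, from fail to pass. None turns a pass into a fail.

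**Two treated subjects excluded.** With a successes among the two excluded, the result is (S − a)/4, and 3 of 4 are needed. The conclusion changes when S is at most 4 and S − a is at least 3:

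- S = 3, a = 0: 3/6 = 50% fail becomes 3/4 = 75% pass
- S = 4, a = 1: 4/6 = 67% fail becomes 3/4 = 75% pass
- S = 4, a = 0: 4/6 = 67% fail becomes 4/4 = 100% pass

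A pass is not lost here: 5/6 losing two successes is 3/4 = 75%.

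**Three excluded.** Changes now go both ways. For example, 3/6 becomes 3/3 (pass), while 5/6 losing three successes becomes 2/3 = 67% (fail).

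**The figure of six in 7.1.** It is justified there by a paired t-test (difference 200 mm³, SD 50 mm³, power 0.95). Taking 50 as the SD of the difference and a two-sided test, exact power is 0.908 at n = 3, 0.998 at n = 4 and above 0.999 at n = 6. Six is therefore enough for that test, though four would do. The calculation does not address the 75% rule, and this point does not depend on it.

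**The case against.** The strongest reply is that *cases* naturally means attempted openings. Section 3.1 plans six patients in whom opening will be attempted, 7.1 compares scans patient by patient, and 8.5 counts failures to open per subject with no compliance filter. The 7.3 set follows 7.2, whose named test is a paired t-test that needs two scans, so 7.3 may have been meant for that analysis alone. *Randomized* looks like leftover template wording.

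This is a fair reading and may be the intended one, but no sentence says so. If it is intended, stating it costs nothing.

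The routes to exclusion are also narrow. The opening MRI is taken on the treatment day (6.2), so a subject withdrawn later already has that evidence, and nothing says it would be discarded. That stands, and it limits how often the gap would matter. It does not settle how a stopped session counts, or whether a later withdrawal removes the subject from the 7.3 set.

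The rule in 8.5 that three subjects without opening lead to a discussion with the FDA is a partial safeguard. A result of 4/6 has only 6 − 4 = 2 non-successes, so it would not trigger that rule.

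A reader might infer that the plan computes the 75% on compliant subjects, or tabulates safety only for them. Neither is stated, and 8.2 records adverse effects for everyone. A reader might also infer that a subject whose barrier did not open can simply be dropped; nothing in 7.3 supports that.

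**Conclusion.** The point holds as a contradiction between 7.3 and 5.3 plus an undefined denominator in 7.1. The contradiction is certain from the text. The effect on the conclusion is conditional: it needs the compliant-only reading, and at least one treated subject left out as non-compliant. With six treated, one exclusion matters only at 4/6 to 4/5. Two exclusions matter at 3/6 to 3/4, 4/6 to 3/4 and 4/6 to 4/4.

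These are counts of configurations, not probabilities. A reader might infer a chance of false success, but the documents give no stop or withdrawal rate from which to compute one. Nor is the compliant-only reading always the favourable one: 5/6 losing three successes becomes a fail.

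Sections 8.6 and 8.6.1 say that the study is discontinued after a reaction, while 8.5 speaks of stopping treatment, pausing the investigation or ending the session. That wording needs reconciling, as does follow-up after withdrawal in 4.4.2 against 8.2. Both are separate matters, and this point rests on neither.

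It should be fixed, because the plan's only stated population cannot be used as written and the remedy is short.

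**What to change.** - **7.3:** delete *randomized*. Define the primary feasibility and safety population as *all subjects in whom sonication with microbubbles was started*. Keep the protocol-compliant set as a sensitivity analysis.
- **7.1:** state that *cases* means all subjects in that population, and that a subject without MRI evidence of safe opening counts as not successful. This is a convention, chosen because 7.1 already requires the evidence to come from MRI.
- **7.1:** state that a stopped session with a readable MRI stays in the denominator and is judged against a definition of *safely* fixed before the first treatment. Without that definition, such a subject could still be scored either way.

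**Cost:** wording in two sections and one agreed definition, with no added patients or procedures. The downside is that the reported success rate may be lower than on the compliant set.
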